4.6.3 Deaths, Other Serious Adverse Events, and Other Significant Adverse Events

All deaths during the study, including the post-treatment follow-up period, will also be listed by patient, to include the primary cause of death. Serious AEs and other significant AEs, including those that led to study withdrawal, dosing interruption, or dose reduction of either study drug, will be provided in separate patient data listings.

4.6.4 Clinical Laboratory Evaluation

All descriptive summaries of laboratory test results will be based on data analyzed by the central or local laboratories and presented in Système International (SI) units, as suggested by the Center for Biologics Evaluation and Research and the Center for Drug Evaluation and Research *Position on Use of SI Units for Lab Tests* (Oct 2013). All data will be included in by-patient data listings. Laboratory measurements identified as abnormal (i.e., outside the normal range) will also be listed separately by patient, laboratory test, and unit. By-patient data listings of laboratory test abnormalities Grade ≥3 will also be provided. In addition, normal ranges provided by the central or local laboratories will be presented in a separate listing.

Clinical laboratory measurements, including serum chemistry, hematology, and coagulation will be summarized by study phase and cohort. Descriptive statistics will be presented for observed values and changes from baseline at each visit where parameters were scheduled to be collected per the clinical study protocol.

The cumulative number and percentage of patients with liver function test abnormalities meeting drug-induced liver injury (DILI) criteria will be summarized by cohort. Patients meeting DILI criteria will also be presented in a patient data listing.

In addition, creatinine clearance will be calculated by the Cockcroft-Gault formula. For males, the creatinine clearance in mL/min will be calculated as [(140 - age) \times weight (kg)]/[72 \times serum creatinine (mg/dL)]. For females, the creatinine clearance in mL/min will be calculated as $0.85 \times$ the male value. The mean change from baseline over time for creatinine and creatinine clearance will be presented graphically over time by cohort and over all patients combined.

Where applicable, laboratory results will be classified as "low," "normal," or "high" with respect to the parameter-specific reference ranges (i.e., below the lower limit of the normal range, within the normal range, or above the upper limit of the normal range). Three-by-three contingency tables will be presented for each laboratory parameter to summarize the shift from the baseline category to the worst post-baseline measurement, defined as the value numerically farthest outside of the normal range across all post-baseline visits through the end of the study.

Summary results will include the count and percentage of patients within each shift category and cohort.

Where applicable, hematology and chemistry results for selected parameters will be assigned a toxicity grade based on the U.S. Department of Health and Human Services *Common Terminology Criteria for Adverse Events (CTCAE)*, version 5.0 (27 Nov 2017). If criteria for a grade includes a quantitative component and a clinical intervention component, the clinical intervention component will be ignored where it cannot be programmatically addressed using available data and only the quantitative portion of the criteria will be considered. If the quantitative criteria for grading are equivalent for two grades and the differentiation is described by clinical interventions, the clinical intervention component will not be considered and the highest CTCAE grade will be assigned. Similarly, death related to AE (i.e., Grade 5) cannot be determined with available laboratory-based data collection and, thus, will not be

summarized as a category. Laboratory parameters that include multiple sets of criteria for each direction (e.g., separate criteria for potassium measures to assess hyperkalemia and hypokalemia) will be summarized separately to reflect each set of criteria.

Five-by-five contingency tables will be presented for laboratory tests where toxicity grading can be applied, to summarize the shift from the baseline grade to the worst post-baseline grade. Grades will be presented as none (Grade 0; i.e., measurements did not meet any CTCAE criteria for Grades 1 through 4), mild (Grade 1), moderate (Grade 2), severe (Grade 3), or life-threatening (Grade 4). Summary results will include the count and percentage of patients within each shift category.

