	nanatinostat/valganciclovir at the same dose.

Abbreviations: ANC = absolute neutrophil count; CTCAE = Common Terminology Criteria for Adverse Events; G-CSF = granulocyte colony-stimulating factor; GM-CSF = granulocyte macrophage-colony stimulating factor; NCI = National Cancer Institute; PO = orally; QD = once daily.

Patients should be monitored approximately twice weekly for resolution of the toxicity. During a dose interruption, study days and procedures will continue to accrue until the end of the current cycle (see Schedule of Events in Section 6.1). If the dose interruption extends beyond the end of the cycle, the subsequent cycle will not begin until dosing has resumed. If the dose is held for more than 14 days, the Investigator should consult with the Medical Monitor before dosing resumes.

If a patient has multiple dose interruptions for study drug toxicity or has had to interrupt for more than 14 days, a dose reduction should be considered. Re-escalation of study drug dose may only be performed after approval by Medical Monitor.

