#### **5.5.1.1.** Hematopoietic Growth Factors

The prophylactic use of hematopoietic growth factors is prohibited unless the patient experiences an AE. Granulocyte colony-stimulating factor (G-CSF) agents may be administered in response to Grade ≥3 neutropenia (Table 3). The American Society of Clinical Oncology (ASCO) clinical practice guidelines should be followed (Smith 2015). Hematopoietic growth factors may not be used to allow for patient eligibility at screening.

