4.1.2 Summarization by Visit

Data summarized by study visit will be based on the nominal, scheduled visit label as reported on the eCRF. Data collected for the last patient visit will be summarized separately and this summary will be labeled as "End of Treatment" in the analysis.

Data collected at unscheduled visits will not be included in by-visit summaries but will be considered when endpoint derivations potentially include multiple visits (e.g., determination of baseline value, determination of worst post-baseline value, etc.). All data will be included in patient listings.

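### In the low/normal/high laboratory shift table, one worst value is kept regardless of direction, so a large enough neutrophil overshoot hides the nadir in that table

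*SAP*

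**What the plan says.** SAP 4.6.4 plans two kinds of laboratory shift table.

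The first classifies results against the reference range as low, normal or high: "Three-by-three contingency tables will be presented for each laboratory parameter to summarize the shift from the baseline category". The post-baseline side of that table is the "worst post-baseline measurement, defined as the value numerically farthest outside of the normal range across all post-baseline visits through the end of the study". SAP 4.1.2 keeps unscheduled visits out of the by-visit summaries but lets them into derivations that span visits, and gives "determination of worst post-baseline value" as an example.

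The second is a five-by-five table for tests to which CTCAE grading can be applied. Its purpose is "to summarize the shift from the baseline grade to the worst post-baseline grade". For grading, the SAP singles out "Laboratory parameters that include multiple sets of criteria for each direction" and has each set of criteria summarized separately. The three-by-three table has no matching rule.

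On the treatment side, Protocol 5.5.1.1 says that G-CSF "agents may be administered in response to Grade ≥3 neutropenia". Of patients whose dosing is interrupted for toxicity, Protocol 5.4 says: "Patients should be monitored approximately twice weekly for resolution of the toxicity".

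**The concern.** Each patient enters the three-by-three table once per parameter, as low or as high but never both. The choice rests on distance from the range, and the two sides are not symmetrical. A count cannot fall below zero, so the low-side distance can never exceed the lower limit of normal (LLN). Nothing caps the distance above the upper limit (ULN).

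The patients exposed to this are those with severe neutrophil nadirs, because they are the ones who may receive a drug that raises the count. With sampling about twice a week during toxicity and unscheduled values counted, both the nadir and the overshoot can enter the derivation. Neutropenia is also among the most frequent Grade 3/4 events in the prior study: Protocol 1.2.4 reports neutropenia in 12 of 64 patients (18.8%) and neutrophil count decreased in 9 (14.1%), and the two terms may overlap. At stake is whether one planned safety table undercounts low shifts for a main toxicity.

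**Working it through.** The plan states no figure for this rule, so there is nothing to reproduce. The check applies the rule as written, reading distance as absolute distance in reported units, since the SAP defines no other metric.

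**Inputs**
- Selection rule: SAP 4.6.4.
- Grade limits, from Protocol Table 3: Grade 4 neutropenia is ANC below 0.5 × 10⁹/L, Grade 4 thrombocytopenia is platelets below 25 × 10⁹/L, and Grade 3 anemia is hemoglobin below 8.0 g/dL (80 g/L).
- Reference ranges: not in the documents. Assumed for ANC: 1.5–7.0, 1.8–7.5 and 2.0–8.0 × 10⁹/L. Assumed for platelets: 130–370, 150–400 and 150–450 × 10⁹/L. Assumed for hemoglobin: 115–155, 120–160 and 135–175 g/L.

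**Formula**
- Distance of a value v: max(LLN − v, v − ULN, 0).
- A nadir x is displaced by a value y when y − ULN > LLN − x, that is, when y > ULN + (LLN − x).
- Since x ≥ 0, any y > ULN + LLN displaces every possible nadir.

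**Thresholds under the assumed ranges**

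| Parameter | Nadir | Range | Displaced above |
|---|---|---|---|
| ANC | 0.49 | 1.5–7.0 | 7.0 + 1.01 = 8.01 |
| ANC | 0 | 1.5–7.0 | 7.0 + 1.5 = 8.5 |
| ANC | 0 | 1.8–7.5 | 7.5 + 1.8 = 9.3 |
| ANC | 0 | 2.0–8.0 | 8.0 + 2.0 = 10.0 |
| Platelets | 24 | 130–370 | 370 + 106 = 476 |
| Platelets | 0 | 150–400 | 400 + 150 = 550 |
| Platelets | 0 | 150–450 | 450 + 150 = 600 |
| Hemoglobin | 79 | 115–155 | 155 + 36 = 191 |
| Hemoglobin | 60 | 135–175 | 175 + 75 = 250 |

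Across the assumed ranges, a Grade 4 ANC nadir is displaced above about 8.0 to 10.0 × 10⁹/L, or 1.14 to 1.25 × ULN. A Grade 4 platelet nadir is displaced above about 476 to 600 × 10⁹/L, or 1.28 to 1.38 × ULN. A hemoglobin nadir of 60 to 79 g/L would need a value above about 191 to 250 g/L.

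**Worked patients**
- ANC 3.0, 0.3, 12.0 with range 1.8–7.5: low distance 1.8 − 0.3 = 1.5, high distance 12.0 − 7.5 = 4.5. Tabulated as high only.
- ANC 3.0, 0.3, 8.5 with the same range: high distance 8.5 − 7.5 = 1.0, less than 1.5. Stays low.
- Platelets 200, 20, 560 with range 150–400: 130 below against 160 above. Tabulated as high only.
- Platelets 200, 20, 480 with the same range: 130 below against 80 above. Stays low.

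The same arithmetic governs total white cells; no threshold was calculated for them.

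**The case against.** The strongest reply is that severe cytopenia is displayed elsewhere, and this largely stands.

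- The five-by-five table selects by grade, with directions kept apart, so a high value cannot displace a severe low-direction grade.
- SAP 4.6.4 also lists all out-of-range values and all abnormalities of Grade 3 or higher. Protocol 9.7 promises a summary of clinically significant Grade 3 and 4 abnormalities.
- Under Protocol 8.1.1, a laboratory abnormality that needs treatment or interruption of study drug is an adverse event. Protocol Table 3 interrupts dosing for Grade 4 neutropenia. A patient with a severe nadir who receives G-CSF therefore meets the definition and enters the SAP 4.6.2 tables by highest CTCAE grade; an interruption enters the dose-interruption tables too.
- The three-by-three table does not measure severity. Under the assumed lower limits of 1.5 to 2.0, an ANC of 1.4 and one of 0.1 are both simply low.

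A reader might therefore go too far in inferring that severe cytopenia drops out of the safety report, or that all the shift tables understate it. The documents do not support that. Nor does every recovery erase a nadir: a value inside the normal range has distance zero and displaces nothing, and a modest overshoot, as in the second ANC example, leaves the patient low. A potassium case can be built on an assumed range of 3.5–5.0 (2.8 is 0.7 below, 5.8 is 0.8 above), but potassium is the SAP's own example of a test graded separately by direction.

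What the reply does not remove is the wrong count in the three-by-three table. Listings do not correct a summary. CTCAE grading covers selected parameters that the SAP does not name, so coverage of neutrophils and platelets is likely but not stated. Fewer low neutrophil shifts in one table than in the other would also need explaining in the report.

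**Conclusion.** The point holds for the three-by-three table only. Whenever a value above ULN lies farther from the range than the nadir does, the rule counts the patient as a shift to high and drops the low shift. The bias runs one way for counts, because only the low side is bounded. It is realistic mainly for neutrophils and white cells after permitted G-CSF, unlikely for platelets, and not realistic for hemoglobin.

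The thresholds rest on assumed reference ranges and on reading the rule as absolute distance. The number of patients affected cannot be computed from the documents. No endpoint, stopping rule or dose decision is tied to this table, and the severe event remains visible in the displays listed above. Severity is minor.

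**What to change.** In SAP 4.6.4, delete the farthest-value rule for parameters with both limits. Replace it with two shift tables per parameter: baseline category to lowest post-baseline category, and baseline category to highest. The patient with ANC 3.0, 0.3 and 12.0 would then appear as a shift to low in the first and to high in the second. While editing the section, name the parameters that will be CTCAE-graded, so that the reader can see that neutrophils and platelets are covered.

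The cost is SAP wording, some programming and more table rows. No new data are needed. SAP Section 1 says the plan is to be final before any formal interim or final analysis, so the change belongs before that point.

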4.6.5 Vital Signs, Physical Findings, and Other Observations Related to Safety

4.6.5.1 Vital Signs

Descriptive statistics for vital sign parameter measurements will be presented for results and change from baseline at each visit where parameters were scheduled to be collected.

4.6.5.2 12-Lead Electrocardiogram

Descriptive statistics for 12-lead ECG interval parameters will be presented for observed values and changes from baseline at each visit where parameters were scheduled to be collected. All ECGs will be performed in triplicate, and the mean of these triplicate measurements at each time point will be used for summarization.

Twelve-lead ECGs will be classified by the investigator as "normal," "abnormal," "not clinically significant," or "abnormal, clinically significant." The worst classification for each set of triplicate 12-lead ECGs will be used for analysis. Three-by-three contingency tables will be presented to summarize the shift from the baseline category to the worst post-baseline value. Summary results will include the count and percentage of patients within each shift category and cohort.

Prolonged QTcF will be summarized as QTcF measurements (msec) that are >450, >480, and >500 msec averaged over each set of triplicate 12-lead ECGs at each visit where ECG is routinely collected per the clinical study protocol. Change from baseline categories will also be summarized for measurements that represent a change >30 or >60 msec relative to the baseline value. Summary results will include the percentage of patients within each category and cohort.

Clinically significant abnormalities occurring at any point in the study post-baseline will be presented in patient data listings.

4.6.5.3 Physical Examination

Results of physical examinations will be presented in patient data listings by patient, study visit, and body system. Any findings during symptom-directed exams will be reported as AEs.

4.6.5.4 ECOG Performance Status

Performance status will be assessed using the ECOG scale. Descriptive statistics will be presented for observed values and changes from baseline at each visit where assessments were scheduled to be collected per the clinical study protocol. Results will be presented in patient data listings.

4.6.5.5 Viral Levels

Viral levels [EBV, CMV, HHV-6, HHV-8, and HIV (for HIV+ patients only)] will be monitored for viral reactivation. Results will be presented in patient data listings only.

4.6.5.6 Prior and Concomitant Medications

Medications will be coded using the World Health Organization Drug Dictionary Enhanced (WHODDE), version March 1, 2023. Medications entered on the eCRF will be mapped to Anatomical Therapeutic Chemical (ATC) drug class (level 4) and drug name.

Prior and concomitant medications will be summarized separately, and the categorization of each medication will be determined programmatically based on medication start and end dates. A prior medication is defined as any medication administered prior to the date of the first dose of study drug with an end date prior to date of first dose of study drug. A concomitant medication is defined as any medication administered on or after the date of the first dose of study drug through 28 days after the last dose of study medication. Any medication whose start date/time cannot be determined due to partial or missing medication start and/or end dates will be considered a concomitant medication.

For both prior and concomitant medications summaries, the number and percentage of patients receiving any medication will be summarized by cohort, as will the number and percentage receiving any medication by ATC drug class and generic drug name. Prior medications will also be summarized over all patients combined. Patients reporting use of more than one medication at each level of summarization (any medication received, ATC class, and generic drug name) will be counted only once. ATC class terms will be displayed by descending order of incidence, as will generic drug names within each ATC class. The study phase during which each medication was received (e.g., prior, concomitant, or both) will be presented on the listing of prior and concomitant medications.

4.7 Determination of Sample Size

This multinational, multicenter study will employ a Simon's optimal 2-stage design to allow termination of enrollment into cohorts where treatment appears futile (Simon 1989). The decision to transition from Stage 1 to Stage 2 is dependent on the assumption of ORR: ORR \leq 10% (poor response); ORR \geq 35% (good response). The sample size estimation uses 1-sided alpha = 0.05 and targets statistical power = 85%.

Using the Simon's 2-stage design approach, the null hypothesis that the true response rate is 10% will be tested against a one-sided alternative. In the first stage, up to 10 patients will be accrued in each cohort. If there are 1 or fewer responses, the cohort will

be discontinued. If the cohort fails to enroll any patients within 1 year from the enrollment of the first patient, the cohort will be considered for termination of enrollment. Otherwise, if at least 2 patients in a cohort respond, additional patients will be accrued for a total of 21 in the cohort. The null hypothesis that the true response rate is 10% will be rejected in each cohort where 5 or more responses are observed in 21 patients. This design yields a type I error rate of 0.0440 and power of 86.2% within each cohort where the true response rate is 35%.

If 10 patients of a given lymphoma subtype are enrolled into Cohort 7, then the Simon's decision criteria will be applied to determine whether or not to add patients in Stage 2 for that subtype. If none of the subtypes represented in Cohort 7 enrolls at least 10 patients, efficacy data collected on those patients will be listed, but not summarized by group. All patients will be summarized for safety, regardless of the decision to discontinue enrollment into any cohort.

If at the end of Stage 2 there are at least 7 responders observed in the initial 21 patients in any cohort (ORR \geq 33.3%), enrollment will be expanded to include up to 120 additional patients in that cohort (N=141), with an interim analysis in that cohort to be performed as described in Section 4.5.6.3. Simon's Stage 2 estimate was ORR=33.3% for the PTCL cohort. Using Clopper-Pearson Exact confidence interval approach, the sample size for a 95% CI that would exclude 25% if the ORR was 33.3% was N=120. Using ORR=35%, the minimum sample size is estimated to be N=85.

A formal interim analysis will be performed for each post-Stage 2 expanded lymphoma subtype cohort in patients with second-line EBV⁺ lymphoma when a total of 40 second-line EBV⁺ lymphoma patients have been followed for at least 6 months or permanently discontinued study treatment. The rationale for selecting 40 patients at the interim analysis is provided in Table 4 below using the Clopper-Pearson binomial confidence intervals of the proportion (Clopper 1934).

Table 4 Sample Sizes for the Interim and Final Analyses of Patients with Second-Line EBV⁺ Lymphoma

Sample Size	Observed Rate	95% CI	Control Rate
	42.5%	(59%, 27%)	25%
40	52.5%	(68%, 36%)	35%
	65%	(79%, 48%)	45%
	40%	(55%, 26%)	25%
50	50%	(64%, 36%)	35%
	62%	(75%, 47%)	45%
	38%	(52%, 26%)	25%
60	48%	(61%, 35%)	35%

Sample Size	Observed Rate	95% CI	Control Rate
	60%	(72%, 46%)	45%

If the observed effect is 52.5% (i.e., 21 responders out of 40 patients) at the interim analysis, then the 95% CI will exclude an ORR effect size of 35%. For these interim analyses, the observed ORR by IRC will be evaluated along with 95% CI. Other secondary endpoints will be evaluated with descriptive statistics such as both point and interval estimates.

The final efficacy analysis will be performed as planned with total 120 patients in the expansion stage of the study. Approximately 50-60 patients with second-line EBV⁺ lymphoma are anticipated to be enrolled at the time of the final analyses. The final analyses will be performed when all patients, including second-line EBV⁺ lymphoma patients, have been followed for at least 6 months or permanently discontinued study treatment.

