## 9.4. Sample Size and Power Considerations

This multinational, multicenter study will employ a Simon's 2-stage design to allow termination of enrollment into cohorts where treatment appears futile (Simon 1989). The decision to transition from Stage 1 to Stage 2 is dependent on the assumption of ORR: ORR  $\leq$ 10% (poor response); ORR  $\geq$ 35% (good response). The sample size estimation uses 1-sided alpha = 0.05 and targets statistical power = 85%.

Using the Simon's 2-stage design approach, the null hypothesis that the true response rate is 10% will be tested against a one-sided alternative. In the first stage, up to 10 patients will be accrued in each cohort. If there are 1 or fewer responses, the cohort will be discontinued. If the cohort fails to enroll any patients within 1 year from the enrollment of the first patient, the cohort will

be considered for termination of enrollment. Otherwise, if at least 2 patients in a cohort respond, additional patients will be accrued for a total of 21 in the cohort. The null hypothesis that the true response rate is 10% will be rejected in each cohort where 5 or more responses are observed in 21 patients. This design yields a type I error rate of 0.0440 and power of 86.2% within each cohort where the true response rate is 35%.

If 10 patients of a given lymphoma subtype are enrolled into Cohort 7, then the Simon's decision criteria will be applied to determine whether or not to add patients in Stage 2 for that subtype. If none of the subtypes represented in Cohort 7 enrolls at least 10 patients, efficacy data collected on those patients will be listed, but not summarized by group. All patients will be summarized for safety, regardless of the decision to discontinue enrollment into any cohort.

If at the end of Stage 2 there are at least 7 responders observed in the initial 21 patients in any cohort (ORR  $\geq$ 33.3%), enrollment will be expanded to include up to 120 additional patients in that cohort (N=141), with the possibility of performing an interim analysis in that cohort to be described in the statistical analysis plan. The maximum sample size estimated for the expanded cohort is dependent on the assumption of ORR  $\geq$ 35% with the lower bound of its 95% CI excluding ORR 25%.

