4.1.1 Reporting Conventions

The Simon 2-stage and post-Stage 2 expansion parts of the study will be analyzed separately. For safety analyses only, all patients who receive combination therapy over the course of the study will also be analyzed separately.

Tables and figures will be summarized by cohort within each part. A more detailed description for how these data will be presented for each type of analysis (e.g., safety, efficacy, etc.) is provided in subsequent sections herein. In general, all data collected and any derived data will be presented in patient data listings for all enrolled patients. Listings will be ordered by phase, site, cohort, patient number, and assessment or event date. The cohort presented in listings will be based on the planned assignment, unless otherwise noted.

In general, continuous variables will be summarized to indicate the study population sample size (N), number of patients with available data (n), mean, SD, median, first (Q1) and third (Q3) quartiles, minimum, and maximum values. Categorical variables will be summarized by the population size (N), number of patients with available data (n), number of patients in each category, and the percentage of patients in each category. Unless otherwise noted, the denominator to determine the percentage of patients in each category will be based on the number of patients with available data. Select ordinal data may be summarized using both descriptive statistics and counts and percentages of patients in each category, as appropriate.

Non-zero percentages will be rounded to one decimal place. Rounding conventions for presentation of summary statistics will be based on the precision of the variable of summarization, as it is collected in its rawest form (i.e., on the electronic case report form [eCRF] or as provided within an external file) and are outlined as follows:

- The mean and median will be rounded to one more decimal place than the precision of the variable of summarization;
- Measures of variability (e.g., SD, SE) will be rounded to two more decimal places than the precision of the variable of summarization; and
- Minimum and maximum values will be presented using the same precision as the variable of summarization.

Other statistics (e.g., CIs) will be presented using the same general rules outlined above or assessed for the most appropriate presentation based on the underlying data.

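### SAP 4.7's N=120 just misses the property stated for it (40/120 gives a lower limit of 24.994%), and Protocol 9.4 rests the same expansion on a different ORR

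*SAP*

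**What the plan says.** Both documents plan the same enrolment. If at least 7 of the first 21 patients in a cohort respond, "enrollment will be expanded to include up to 120 additional patients in that cohort (N=141" in total).

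The reasons given for that size differ.

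- **Protocol 9.4** (repeated in the synopsis): "The maximum sample size estimated for the expanded cohort is dependent on the assumption of ORR" of at least 35%, "with the lower bound of its 95% CI excluding ORR 25"%. It names no interval method for this calculation and gives no separate N.
- **SAP 4.7**: the starting point is that the "Stage 2 estimate was ORR=33.3% for the PTCL cohort". Then, "Using Clopper-Pearson Exact confidence interval approach", "the sample size for a 95% CI that would exclude 25% if the ORR was 33.3% was N=120". It adds: "Using ORR=35%, the minimum sample size is estimated to be N=85".

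On the denominator, SAP 4.1.1 says that "The Simon 2-stage and post-Stage 2 expansion parts of the study will be analyzed separately", and SAP 4.7 bases the final efficacy analysis on the 120 expansion patients. SAP 3.3.2, however, says the final analysis also covers the entire cohort, in the same paragraph that gives the cohort as 141. SAP 4.8 lists the departures from the protocol, and the sizing basis is not among them.

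**The concern.** The sentence in SAP 4.7 is the only reason the SAP gives for the size of what could be the largest part of the trial. It makes a checkable claim about a whole number of patients, and that claim fails at the stated N. A reader who goes to the protocol for confirmation finds a different ORR. Under the SAP's own figure, that ORR would justify 85 patients rather than 120.

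The Simon stages come with a type I error and a power. The expansion comes with neither. Someone who takes 33.3% or 35% as a true rate could believe that 120 patients make exclusion of 25% likely. The documents give no figure to correct that impression.

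**Working it through.** **Inputs.** Two-sided 95% Clopper-Pearson interval, rate to exclude 25%, ORR 33.3% with N=120, and ORR 35% with N=85 (all SAP 4.7). ORR of at least 35% and total N=141 (Protocol 9.4).

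**Formula.** For x responders in n patients, the lower limit L(x, n) is the 2.5th percentile of a Beta(x, n − x + 1) distribution. L exceeds 25% exactly when P(X ≥ x | n, 0.25) is below 0.025.

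**1. Reproducing the plan's figures.** Let x = ORR × n without rounding to whole patients, and find the smallest n with L above 25%.

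- ORR 1/3: n = 121 (stated 120).
- ORR 0.35: n = 86 (stated 85).

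Both stated sizes reproduce to within one patient, so the SAP's method is clear and sizing is on an assumed observed rate.

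**2. Whole patients.** 120 × 1/3 = 40 exactly.

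| x/n | Rate | Lower limit | Excludes 25%? |
|---|---|---|---|
| 40/120 | 33.3% | 24.994% | No |
| 41/120 | 34.2% | 25.8% | Yes |
| 42/120 | 35.0% | 26.5% | Yes |
| 41/123 | 33.3% | 25.1% | Yes |
| 29/85 | 34.1% | 24.2% | No |
| 30/85 | 35.3% | 25.2% | Yes |
| 46/141 | 32.6% | 24.97% | No |
| 47/141 | 33.3% | 25.6% | Yes |

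Cross-check: P(X ≥ 40 | 120, 0.25) = 0.0251, just above 0.025. The shortfall at 40/120 is 25 − 24.994 = 0.006 percentage points.

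The denominator matters at this margin: an observed 33.3% misses with 120 analysed and succeeds with 141.

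**3. The two bases side by side.** The protocol's 35% gives 86 by step 1 and 85 by the SAP's statement. Neither is 120 or 141. The SAP's 120 comes from 33.3%.

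**4. Probability that the lower limit exceeds 25%.** This is the binomial probability of reaching the smallest count that works.

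| Analysed N | Count needed | True ORR 33.3% | True ORR 35% |
|---|---|---|---|
| 120 | 41 | 45.7% | 61.0% |
| 141 | 47 | 53.2% | 69.0% |

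**5. Sensitivity to the analysed number.** SAP 4.2 makes the primary set the mITT set: patients who were dosed and whose subtype was confirmed by central pathology. Protocol 7.1.6 keeps patients on study when central review disagrees, so fewer than 120 may be analysed. With one exclusion, 40/119 (33.6%) has a lower limit of 25.2%, and 40 responders are then enough.

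**The case against.** The best defence is that 24.994% is 25.0% to one decimal, that the SAP writes a rounded 33.3%, and that its other limits are shown as whole percentages. That stands as to size: this is a gap of about one patient, not a failed calculation. It does not make the sentence true, because responders are counted in whole patients and 40 of 120 does not exclude 25%.

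A second defence is that the protocol's statement holds at the planned size, since 42/120 excludes 25%, and that the SAP supersedes the protocol's analysis plan. Both are correct. Neither explains why the same enrolment is attributed to two ORRs, one of which the SAP says needs only 85 patients.

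Three stronger readings are tempting, and the documents do not support them.

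- **The documents plan different sample sizes.** They do not. Both state up to 120 additional patients and 141 in total.
- **141 can never be the denominator.** SAP 4.1.1 and 4.7 point to 120, but the reference in SAP 3.3.2 to the entire cohort leaves the matter ambiguous.
- **The trial would misjudge success at 40 responders.** No success count is attached to the 120. SAP 4.5.6.5 calls the results descriptive, with no hypothesis testing planned, and SAP 4.5 places the primary expansion analyses in the second-line subgroup, which has its own Table 4.

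Nor do the 46% and 61% figures show an arithmetic error. A probability near one half is what sizing on an observed rate produces when the true rate is close to the threshold.

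**Conclusion.** The point holds in limited form. The property that SAP 4.7 states for N=120 is not met at 33.3%, by 0.006 percentage points or about one patient. Protocol 9.4 and the synopsis give a different ORR basis for the same enrolment, a basis that by the SAP's own figure leads to 85, and SAP 4.8 does not record the change. The conflicting basis is the more important part, because it does not depend on rounding.

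This rests on a two-sided 95% Clopper-Pearson interval, on 33.3% meaning one third, and on all 120 expansion patients being analysed. The probabilities further assume independent responses at a common true rate. No enrolment number or decision rule in the plan is shown to be wrong. What needs correcting is the stated justification, so that a reader knows what 120 patients can and cannot show.

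**What to change.** Amend Protocol 9.4, the matching synopsis text and SAP 4.7 so that they agree.

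1. Use one ORR basis in both documents. If the SAP's basis is kept, list it in SAP 4.8 as a departure from the protocol until the protocol is aligned.
2. Say whether the sizing refers to the 120 expansion patients or to all 141, and make SAP 3.3.2, 4.1.1 and 4.7 consistent with that choice.
3. Say that 33.3% and 35% are observed rates.
4. Replace the N=120 sentence with a conditional one: if 120 patients are analysed, the lower 95% limit exceeds 25% from 41 responders (34.2%), with the count recomputed for the actual mITT number (for example, 40 of 119). Do not fix 41 as a threshold. If the 35% figure is kept, give 86, or say that 30 of 85 works and 29 of 85 does not.
5. Report the probability of excluding 25%: about 46% at a true ORR of 33.3% and 61% at 35% with 120 analysed (53% and 69% with 141).

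The cost is a change of text. Enrolment and conduct are unaffected. The stated justification becomes slightly less favourable.
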